Eplerenone for Central Serous Chorioretinopathy: A Pilot Study

Protocol

IRB#: 10722

Principal Investigator: [name]

Co-investigators: [name], [name], [name], [name], [name], [name], [name], [name]

Coordinators: [name], [name], [name]

Part I

Aim and Hypotheses:

We would like to examine the short-term effects and safety of a systemic anti-aldosterone medication, eplerenone, in a small group of patients with central serous chorioretinopathy (CSCR), an idiopathic eye disease which affects the central vision and is known to be worsened or potentiated by elevated systemic corticosteroid levels.

In rat eyes, mineralocorticoid challenges have been shown to cause similar changes in the retina and choroid (choroidal vessel vasodilation, focal leakage, and increased choroidal thickness) as found in human patients with CSCR, suggesting that mineralocorticoids may play a role in potentiating CSCR.[1] Eplerenone, a mineralocorticoid receptor antagonist, has been shown to be of visual and anatomic benefit in a small retrospective series of 4 patients with chronic CSCR, suggesting that decreasing mineralocorticoid action in the eye may improve signs and symptoms of CSCR.[1] This data is enticing, and is the only current published evidence that eplerenone may be used to treat CSCR. However, in their study, the investigators only evaluated patients with chronic CSCR, and did so in a retrospective and uncontrolled fashion in only 4 patients.[1]

Our aim is to evaluate a standardized dose of eplerenone in a controlled prospective fashion for both acute and chronic CSCR. We hypothesize that aldosterone inhibition with eplerenone will decrease choroidal vessel vasodilation, focal leakage, and choroidal thickness in patients with both acute and chronic CSCR, leading to resolution of subretinal fluid and ultimately an improvement in symptoms. Sub-retinal fluid can be precisely measured using optical coherence tomography (OCT), an imaging technique discussed below.

Background:

Epidemiology of CSCR

Central Serous Chorioretinopathy (CSCR) is a disease of the choroid and retina that causes subretinal fluid to accumulate in the macula, the central and most important part of the retina.[2] CSCR is the fourth most commonly observed disease in a typical clinical practice of retinal disorders, after macular degeneration, diabetic retinopathy, and retinal vein occlusion, and affects 1 in 10,000 individuals over their lifetime.[3] Because of the involvement of the macula, CSCR causes distortion and blurring of

central vision.[2] It is most commonly idiopathic in nature, although CSCR has been associated with both exogenous (e.g., anabolic or prescribed corticosteroids, intra-articular corticosteroid injections, inhaled corticosteroids) and endogenous (e.g., Cushing's disease, etc.) increases in serum corticosteroid levels.[4] Systemic hypertension has also been associated with CSCR.[5] CSCR has been associated with high stress, and is more common in men.[2,6] CSCR typically affects people of middle-age, although it can occur in patients younger than 20 and older than 60 as well.[7] In the U.S., the disease is more common in Asian and Caucasian populations than in other racial groups.[8]

Prognosis of CSCR

There are two forms of the disease, acute CSCR and chronic CSCR.[8] In the acute phase, there is rapid accumulation of subretinal fluid in the macula. The fluid is then resorbed spontaneously, typically over 6-12 weeks.[8-11] Importantly for our study, only about 20% of patients with acute CSCR have complete resolution of fluid on OCT by 1 month. This was shown in randomized studies by Chan et al (4 of 19 patients) and Ratanasukon et al (6 of 29 patients).[12,13] Another study of 20 patients with acute CSCR showed the mean time to complete resolution of subretinal fluid on OCT was 65 days (range, 28–155).[14] In our clinical experience at Tufts, 10% or less of patients have complete resolution of subretinal fluid on OCT by 1 month after presentation.

Of note, even after fluid resorption, visual changes may still be reported by patients for several months after the initial episode.[15] The definition of chronic CSCR has not been agreed upon, but most of the literature defines it as sub-retinal fluid lasting more than 3 months, or recurrence of the disease within 1 year.[8-12] Chronic CSCR is also more likely to be bilateral, while acute CSCR more typically affects one eye at a time. Approximately 30-50% of all CSCR patients have recurrences of the disease, either in the same eye, opposite eye, or both eyes.[8,12] Patients with chronic CSCR can also develop intra-retinal fluid in addition to sub-retinal fluid.

Pathophysiology of CSCR

The pathophysiology of CSCR remains unclear, but recent studies using specialized imaging techniques have been helpful. CSCR is thought to be caused by an underlying abnormality in vascular permeability in the choroidal vessels, leading to elevation of the retinal pigment epithelium (RPE) from Bruch's membrane. The separated RPE may then undergo tiny rips, leading to direct connection between the choroid and the subretinal space. The RPE pump, which usually prevents accumulation of fluid under the retina, then dysfunctions or is overwhelmed, leading to build-up of serous fluid under the retina, the typical and characteristic feature of CSCR.[8,12] The abnormality in choroidal circulation is often bilateral. A familial predisposition is occasionally observed, although no clearly-defined pattern of inheritance has been elucidated.

Imaging in CSCR

Specialized imaging techniques are typically used to diagnose and follow patients with CSCR. Fluorescein angiography (FA) is the gold standard to diagnose the disease. The most characteristic finding is an expanding point of fluorescein leakage under the neurosensory detachment of the macula, seen in approximately 90% of patients.[8] Multiple points of leakage can be seen in some patients, particularly in chronic CSCR.[16] FA can be used to direct focal laser photocoagulation treatment or photodynamic therapy (both discussed below).

Optical coherence tomography (OCT) is also useful in diagnosing CSCR, and can be very helpful in monitoring disease activity over time. OCT takes images of the macula in cross-section with very high resolution (~5 um), allowing precise visualization and quantification of retinal thickness and amount of subretinal fluid over time. OCT can also demonstrate focal RPE detachments in patients with CSCR, in both affected and unaffected eyes.[17,18] Special OCT imaging protocols, called Enhanced Depth Imaging (EDI), allow improved visualization of choroidal thickness, which has been shown to be significantly thicker in patients with CSCR than in age-matched controls.[19] In patients with chronic CSCR, OCT can sometimes demonstrate intraretinal fluid in addition to subretinal fluid.

Other specialized imaging modalities, such as indocyanine green angiography (ICGA) and fundus autofluorescence, can also be used to help with the diagnosis.[8] Fundus autofluorescence detects subtle changes in the RPE, which can be affected in characteristic patterns in CSCR. ICGA highlights choroidal circulation, and can be particularly helpful for directing focal laser treatment or photodynamic therapy (both discussed below).

Treatment of CSCR

There have been few randomized trials looking at treatment of CSCR, and there is no gold standard for therapy. Without treatment, many patients have spontaneous resolution of fluid within three months of diagnosis. Focal laser photocoagulation has been used for treatment of some patients with acute CSCR. Studies suggest that this can hasten fluid resorption and decrease the rate of recurrence, but does not alter long-term visual prognosis.[20,21] Laser can only be used if there's a localized area of leakage on fluorescein angiography away from the center of the macula. Laser burns almost always leave a retinal scar and can result in a permanent scotoma. The scar can also lead to secondary formation of choroidal neovascularization. Therefore, focal laser is only advisable in select patients.[8]

Photodynamic therapy (PDT) is another type of laser treatment that was originally developed (and is FDA-approved) for neovascular age-related macular degeneration. PDT involves injecting a light-activated dye, verteporfin, intravenously, and then directing a "cold" laser to the region of interest in the retina. PDT offers a more directed treatment to the abnormal choroidal vessels, and can be targeted to the central macula as well as to multiple areas of leakage on fluorescein angiography. PDT has been used successfully in treating both acute and chronic CSCR.[12,22,23] In a randomized trial by Chan *et al* examining PDT for acute CSCR, 80% of patients (31 of 39) had complete resolution of fluid in the PDT arm one month after treatment, versus 20% of patients (4 of 19) in the control arm.[12] A number of trials have used PDT in

chronic CSCR, and the treatment seems to resolve fluid on OCT by one month in 50-100% of patients.[8,22-26]

However, PDT has a number of side effects, and it is not FDA-approved for the treatment of CSCR. Side effects include RPE changes, choriocapillary hypoperfusion, and choroidal neovascular membrane development, as well as severe skin reactions.[23] To decrease some of the ocular side effects, researchers have attempted to decrease the power of laser used; this is called “low-fluence” PDT. Small comparative studies suggest that low-fluence PDT is as effective as standard-fluence PDT, with fewer ocular side effects.[25,26] Most retina specialists now consider using low-fluence PDT for treatment of chronic CSCR.

A number of other small studies have shown possible benefits from a variety of systemic medications for acute and/or chronic CSCR, including steroid hormone antagonists (ketoconazole, mifepristone, eplerenone, finasteride),[1,27-29] adrenergic receptor antagonists (metoprolol, propranolol),[30,31] and carbonic anhydrase inhibitors (acetazolamide).[32] The most promising results seem to be with steroid hormone antagonists: finasteride, mifepristone, and eplerenone. Eplerenone is of particular interest, as this medication does not have as many anti-testosterone side effects as the other two agents.

Eplerenone for CSCR

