Eplerenone is a relatively safe medication, but it can lead to raised serum potassium levels (i.e., hyperkalemia), which can be potentially life-threatening. In a large clinical trial of patients with CHF, the incidence of serious hyperkalemia, defined as a serum potassium concentration ≥ 6 mEq/L, was 5.5% in the eplerenone group and 3.9% in the placebo group. Patients with a lower creatinine clearance at baseline had a higher incidence of serious hyperkalemia.[37]

Eplerenone comes in two doses, 25 mg and 50 mg. The standard dose for treatment of hypertension is 50 mg daily. For patients with an inadequate blood pressure response to 50 mg, the dosage is increased to 50 mg twice daily. For treatment of CHF, patients are started on 25 mg, and escalated to 50 mg within four weeks. Dose adjustment in CHF patients takes place based on serum potassium levels as follows: < 5.0 mEq/L – Increase to 50 mg once daily; 5.0 – 5.4 mEq/L – Maintain dose; 5.5 – 5.9 mEq/L – Decrease to 25 mg every other day; ≥ 6.0 mEq/L – Withhold and restart at 25 mg every other day when potassium levels fall to < 5.5 mEq/L.[38]

The other notable side effects with aldosterone-receptor antagonist medications are related to cross-reactivity with sex hormone receptors. Eplerenone has a much lower incidence of anti-sex hormone effects than spironolactone. With eplerenone, sex hormone-related events, such as breast enlargement in men, breast pain, or menstrual abnormalities, have been reported in up to 2.5% of patients, although some studies reported no such events.[39-41]

Because of the elevations in serum potassium concentrations and consequent increased risk for hyperkalemia with eplerenone, use of this drug is contraindicated in patients at increased risk for hyperkalemia, including those with a serum potassium concentration > 5.5 mEq/L, type 2 diabetes and microalbuminuria, a serum creatinine concentration > 2 mg/dL in men and > 1.8 mg/dL in women, or a creatinine clearance < 50 mL/min, and during concomitant administration of potassium supplements, potassium-sparing diuretics, and/or potent CYP3A4 inhibitors.[38] It is recommended to check serum potassium and creatinine before initiating eplerenone therapy, followed by serum potassium within the first week and at one month after the start of treatment.[38]

Part II

Experimental Protocol:

Study Design

[figure not shown]
- Prospective, consecutive, non-randomized, non-blinded, non-comparative interventional pilot study

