- Eligible patients will be those who present with CSCR, both acute and chronic types
- 20 patients will be enrolled; participation is voluntary and all interested patients must provide written informed consent to take part in the study

- Chronic CSCR will be defined as persistent subretinal fluid on OCT ≥ 3 months after initial presentation to the eye clinic, and $< 50\%$ reduction in fluid thickness on OCT after 3 months.
- Only one eye of a participant will be included in the study, although both eyes will be evaluated. In patients with bilateral CSCR, the worse eye will be the study eye.
- Patients will be evaluated and treated at the New England Eye Center (NEEC)
- All participants will receive a standard ophthalmic examination as well as color fundus photographs, fluorescein angiography, and macular OCT (see below for specific imaging protocol).
- Treatment will be the standard dose of eplerenone, 50 mg pills taken one pill daily over four weeks
- Subjects participation will include 4 visits to the NEEC:
 - o Treatment initiation
 - o 1 week after initiation
 - o 2 weeks after initiation
 - o 4 weeks after initiation
- Prior to initiating treatment, all subjects will have laboratory testing to confirm healthy ranges of the following lab tests will include: serum potassium, creatinine, electrolytes, liver function tests, uric acid, and fasting cholesterol.
- Serum potassium and creatinine levels will be re-tested at the 1 week visit.
- All lab tests will be repeated at the 4 week visit
- Blood pressure will be measured at each visit
- A database of enrolled participants will be maintained on a password protected desktop computer at the New England Eye Center.
- When the study is complete, all data will be de-identified and coded.

Study Assessments/Schematic

Study Protocol

-4 to 5 weeks total
 -20 patients with CSCR (Acute or Chronic)

Initial Diagnosis and Enrollment

1. In order to diagnose CSCR, patients typically undergo a routine ophthalmic examination, fundus photographs, fluorescein angiography, and OCT images. Patients may undergo fundus autofluorescence testing or indocyanine green angiography at the discretion of the physician to confirm the diagnosis of CSCR. These tests are done routinely in the eye clinic and are not included as part of the study protocol.

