Both male and female participants of any race will be enrolled.

Inclusion Criteria:

1. Age 18 or over
2. Ability to give written informed consent
3. Presence of sub-retinal fluid under the fovea as seen on OCT
4. Diagnosis of Acute or Chronic CSCR:
 - a. Acute CSCR: First presentation to eye clinic with visual symptoms, including decreased vision or visual distortion, and the characteristic appearance of CSCR on examination, fluorescein angiography, and OCT.
 - b. Chronic CSCR: Previous diagnosis of CSCR, persistent subretinal fluid on OCT \geq 3 months after initial presentation to the eye clinic, and <50%

reduction in fluid thickness on OCT after 3 months. *Patients who have had previous treatment for CSCR may be included.*

Exclusion Criteria:

1. Age less than 18
2. Persons with impaired decision-making ability.
3. Women who are known to be pregnant or are actively trying to conceive.
4. Additional eye disease affecting the macula or posterior retina.
5. At screening, serum potassium concentration ≥ 5.0 mEq/L, a serum creatinine concentration >2 mg/dL in men and >1.8 mg/dL in women, or a creatinine clearance <50 mL/min, and during concomitant administration of potassium supplements, potassium-sparing diuretics, and/or potent CYP3A4 inhibitors (amifostine, cyclosporine, fluconazole, itraconazole, ketoconazole, mifepristone, posaconazole, potassium salts, Rituximab, tacrolimus, voriconazole, nefazodone, troleandomycin, clarithromycin, ritonavir, or nelfinavir).
6. Patients with type 2 diabetes will be screened for microalbuminuria with a urinalysis. If microalbuminuria is present, these patients will be excluded.

Data Elements

The data elements to be collected from each participant include age, gender, visual acuity, intraocular pressure, lens status, and retinal examination findings, color fundus photographs, fluorescein angiography images, and OCT images.

Primary Outcome

Presence or absence of subretinal fluid and/or intraretinal fluid on OCT after 4 weeks of treatment with 50 mg of eplerenone.

Secondary (Exploratory) Outcomes

- Change in central macular circle thickness on OCT, automatically calculated with OCT software after 1, 2, and 4 weeks of treatment
- Change in thickness of subretinal fluid under the fovea on OCT, manually calculated after 1, 2, and 4 weeks of treatment
- Change in thickness of choroid under the fovea on enhanced-depth imaging OCT, manually calculated, after 1, 2, and 4 weeks of treatment

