Changes in continuous secondary outcome measures will be described using mean, median, min/max, and standard deviations, and categorical secondary outcome measures will be described using frequencies and proportions.

Sample Size and Precision Calculations

The natural history of acute CSCR is to improve on its own. Studies have shown, however, that fluid resolution typically takes at least 6 weeks, and often takes as long as 3 months or longer. In a randomized study by Chan et al examining effects of half-dose photodynamic therapy in patients with acute CSCR, 20% of patients had complete resolution of fluid on OCT after 4 weeks, compared to 80% of patients treated with PDT.[12] Similar rates of complete fluid resolution have been reported after treatment with PDT, as well as in a small sample of patients with chronic CSCR treated with eplerenone.[1, 22-26] Based on these assumptions, a calculation was performed to determine the width of confidence intervals for the proportion of patients successfully

treated with eplerenone. If the treatment is effective for 70% of patients, a sample size of 10 patients will give a 95% confidence interval width of 0.586 that includes a lower bound of 0.348 (see range of widths with sample sizes of 10 and 15 below). The Research Design Center of the Clinical and Translational Sciences Institute at Tufts Medical Center assisted with these calculations.

Numeric Results for Two-Sided Confidence Intervals for One Proportion Confidence Interval Formula: Exact

Confidence Level	Sample Size (N)	Target Width	Actual Width	Proportion (P)	Lower Limit	Upper Limit	Width if P = 0.5
0.950	10		0.586	0.700	0.348	0.933	0.626
0.950	10		0.531	0.800	0.444	0.975	0.626
0.950	10		0.442	0.900	0.555	0.997	0.626
0.950	15		0.487	0.700	0.416	0.903	0.522
0.950	15		0.438	0.800	0.519	0.957	0.522
0.950	15		0.356	0.900	0.637	0.993	0.522

References

Flleiss, J. L., Levin, B., Paik, M.C. 2003. Statistical Methods for Rates and Proportions. Third Edition. John Wiley & Sons. New York.
 Newcombe, R. G. 1998. 'Two-Sided Confidence Intervals for the Single Proportion: Comparison of Seven Methods.' *Statistics in Medicine*, 17, pp. 857-872.

Safety Analysis

Safety data will be presented in tabular format and will be summarized descriptively.

PART III

1. How will participants be recruited?
 Participants will be recruited from the practices of the primary investigator and co-investigators.
2. Number of participants needed?

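### The aim promises a controlled evaluation, but the study is single-arm and reports one pooled proportion with no reference rate in a disease that can clear without treatment

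*Combined protocol and SAP*

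**What the plan says.** Part I, Aim and Hypotheses, notes that the investigators of the only published series "did so in a retrospective and uncontrolled fashion in only 4 patients". The statement of aim follows at once: "Our aim is to evaluate a standardized dose of eplerenone in a controlled prospective fashion for both acute and chronic CSCR".

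Part II, Study Design, describes a "Prospective, consecutive, non-randomized, non-blinded, non-comparative interventional pilot study" in which "20 patients will be enrolled", acute and chronic together. The acute/chronic split is not fixed and appears only as a secondary outcome.

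The Primary Outcome is "Presence or absence of subretinal fluid and/or intraretinal fluid on OCT after 4 weeks of treatment with 50 mg of eplerenone". The Statistical Analysis section describes it by one proportion with its 95% CI. It calls descriptive statistics appropriate for a pilot whose data may help design later, more rigorous trials. It names no comparator, benchmark or breakdown by disease type.

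On the untreated course, the Sample Size section says: "The natural history of acute CSCR is to improve on its own". Prognosis of CSCR, in a sentence flagged as important for this study, says "only about 20% of patients with acute CSCR have complete resolution of fluid on OCT by 1 month". It cites 4 of 19 and 6 of 29 patients, and adds that the clinic's own experience is 10% or less. The Sample Size section then describes the planned proportion as patients *successfully treated* with the drug.

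**The concern.** A reader of the aim expects a comparison, and the design contains none. *Controlled* cannot be read as *standardized*. The sentence already uses *standardized* for the dose, and *controlled* answers a criticism of an uncontrolled series made immediately before. The design repairs the retrospective part of that criticism but not the uncontrolled part.

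This matters because some acute eyes are expected to dry within the observation window without the drug. The protocol gives figures for how many, but those figures stop at the background and planning text. Pooling adds a second difficulty. Acute eyes have a cited spontaneous rate, while chronic eyes are selected for "persistent subretinal fluid on OCT ≥ 3 months after initial presentation to the eye clinic" with limited reduction and have none. The background rate for the pooled proportion therefore depends on a mix that the plan leaves open. At stake is whether the pilot's result can be interpreted, and whether later trials inherit a response rate with no background rate beside it.

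**Working it through.** **Inputs.** N = 20 (Study Design). Cited 1-month clearing in acute disease is 4/19 and 6/29, and 10% or less at the clinic (Prognosis of CSCR). The CI method is exact two-sided 95% (Sample Size section). No spontaneous rate is given for chronic eyes.

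**The plan's own figure.** The exact (Clopper-Pearson) limits for x of n are the 2.5% quantile of Beta(x, n − x + 1) and the 97.5% quantile of Beta(x + 1, n − x). For 7/10 this gives 0.348 to 0.933, width 0.586, as stated. The other five rows of the table also reproduce. The arithmetic is not in question.

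**Reference rate.**
- 4/19 = 21.1%; 6/29 = 20.7%.
- Pooled: (4 + 6)/(19 + 29) = 10/48 = 20.8%, exact 95% CI 10.5% to 35.0%.

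The cited *about 20%* is a fair summary, but it comes from few patients.

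**Dry eyes expected with no drug effect** (number acute × rate, assuming that chronic eyes do not dry spontaneously):

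| Acute patients of 20 (assumed) | at 10% | at 20% |
|---|---|---|
| 20 | 2 | 4 |
| 10 | 1 | 2 |
| 0 | 0 | 0 |

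The clinic's figure is *10% or less*, so the 10% column is a maximum on that source.

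**What an observed result could show at N = 20** (same exact formula):

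| Observed | Exact 95% CI | Lower limit above 20%? |
|---|---|---|
| 4/20 | 0.057 to 0.437 | no |
| 8/20 | 0.191 to 0.639 | no |
| 9/20 | 0.231 to 0.685 | yes |
| 14/20 | 0.457 to 0.881 | yes |

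Against 20%, results up to 8/20 cannot be told apart from the cited course, and results from 9/20 can. If the true fluid-free rate were 40%, the chance of reaching 9/20 is 0.404; at 50% it is 0.748; at 70% it is 0.995.

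**Why the mix matters.** The 20% benchmark fits a wholly acute sample. With 10 acute patients and no spontaneous clearing in the chronic ones, the pooled background would be (10 × 0.20)/20 = 10%, and 8/20 (lower limit 0.191) would lie above it. The same result reads differently under two mixes that the plan equally allows, and the planned report does not show which reading applies.

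**The case against.** The best defence is that this is openly a single-arm pilot. It has no test, no decision rule and no efficacy claim in its analysis text, and it says its data are for designing later trials. That stands. It justifies a descriptive analysis and the absence of a control arm. It does not justify the word *controlled*, or leaving out a reference rate that the protocol calls important for the study.

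The untreated rate is also not ignored in planning. The Sample Size section sets 20% beside 80% with PDT before assuming 70%, and its lower limit of 0.348 at N = 10 exceeds 20%. A large effect would clear the cited course without any change to the plan. The gap lies in the analysis text and concerns modest results.

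Three stronger readings are tempting, and the documents do not support them.

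- *Spontaneous drying will be reported as successful treatment.* The outcome and analysis sections are worded neutrally, as presence or absence of fluid and the proportion without it. The *successfully treated* wording occurs only in the sample-size rationale.
- *Chronic eyes supply their own untreated control through their qualifying scans.* Previously treated patients may enter, so not every chronic eye has an untreated interval, and Data Elements does not say that pre-enrolment scans are collected. The comparison would also favour the drug. Eligibility requires less than 50% reduction after 3 months, so over 12 to 13 weeks the prior change is capped at about 50% × 4/13 = 15% to 50% × 4/12 = 17% of initial thickness per 4 weeks. The change on treatment can reach 100%.
- *10/48 is an established untreated rate.* Treatment of CSCR identifies the 4/19 as a control arm. The documents do not say which arm of the placebo-controlled antioxidant trial the 6/29 came from.

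**Conclusion.** The point holds as an error in the stated design property and a gap in the analysis. The study is prospective and uncontrolled, and its aim should say so. Its single pooled proportion, with no reference rate, cannot separate a modest drug effect from the natural course of acute disease: against the cited 20%, anything up to 8/20 is compatible with that course.

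The expected number of spontaneously dry eyes is about 2 to 4 of 20 if every patient is acute. That is an assumption, and the number falls with the acute share. No figure can be given for chronic eyes. The benchmark rests on small cited samples. It also may not match the treated 4 weeks: acute entry sets no limit on symptom duration, enrolment may be deferred, and screening adds up to a week, so the week-4 OCT can fall more than a month after presentation.

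None of this makes the pilot unsound or requires randomization. It limits what the result can be said to show.

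**What to change.** 1. In the aim, replace *controlled prospective* with *prospective, uncontrolled*. In the Sample Size section, replace the wording that calls patients *successfully treated* with eplerenone by *fluid-free at 4 weeks*.
2. In the Statistical Analysis section, report the fluid-free proportion with its exact 95% CI separately for acute and chronic eyes. Print the acute result beside the protocol's own reference rates: 4/19 (control arm); 6/29, labelled *as cited*, once its arm has been verified; and the clinic's 10% or less. Give the days from presentation to the week-4 OCT, so that any mismatch in time window is visible.
3. State that the result estimates a resolution rate and does not by itself show a drug effect.

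The cost is a few words and one descriptive table, with no extra patients or visits. The drawback is that small strata give wide intervals. With 10 acute patients, for example, the plan's own table shows a width of 0.586 at 70%. The comparison with historical rates also remains descriptive only.
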